2.2. Background

2.2.1. Prevalence of Pain among Patients Treated with Hemodialysis

In the U.S. chronic pain has a prevalence of 11% among adults and was estimated in 2016 to have an annual cost of \$635 billion.¹¹ Due to a high comorbidity burden, chronic pain is even more common among patients undergoing treatment with maintenance hemodialysis.^{12 13} More than half of hemodialysis patients have diabetes mellitus,¹⁴ often with accompanying painful neuropathy, and most patients have ESRD-associated mineral metabolism disorders that predispose to chronic musculoskeletal pain,¹⁵ and to a fracture risk that is 2- to 4-fold higher than that for the general population.¹⁶ Falls are also common among hemodialysis patients; recent reports indicate that 25-30% of hemodialysis patients experience at least one fall per year and 57% of these individuals reported multiple falls.¹⁷

Pain in the setting of ESRD and hemodialysis has some key differences from that experienced by the general population. In addition to chronic pain, patients often experience acute pain associated with recurring hemodialysis sessions (typically 3 per week). Sources of hemodialysis-associated pain include severe muscle cramping resulting from fluid removal, needle infiltrations, vascular steal syndrome and other complications of hemodialysis vascular access, and a “washed out” feeling with substantial fatigue and headaches that may persist for up to 12 hours after dialysis sessions. One recent systematic review estimated that 33-82% and 21-92% of dialysis patients have acute and chronic pain, respectively.¹⁸ An earlier systematic review quantified this as a mean prevalence of pain of 47% across 60 studies, with pain during the hemodialysis treatments, including vascular access pain, headache, neuropathic pain, and musculoskeletal pain, occurring most frequently.¹²

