7.4.2. Contacts with the Research Team (Weeks 4, 8, 12, 16, and 20)

Participants in both randomized groups will be contacted by research coordinators either in person or by telephone every 4 weeks during Phase 1. These contacts will be used for the following:

- Ascertainment of hospitalizations (secondary outcome)
- Ascertainment of falls (secondary outcome)
- Ascertainment of Adverse Events of Interest and SAEs
- Documentation of any change in the participant's opioid prescriber(s)
- Documentation of non-opioid analgesics, antidepressants, anxiolytic and sedatives/hypnotics
- Review of concomitant medications with documentation of initiation of new medications or discontinuation of prior medications
- Documentation of use of non-study behavioral or other non-pharmacologic treatments for pain
- Scheduling of Week 12 or Week 24 CATI calls

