9.1.2. Serious Adverse Event

A *serious adverse event (SAE)* is any AE that is:

- fatal or results in death
- life-threatening
- requires or prolongs hospital stay
- results in persistent or significant disability or incapacity
- results in congenital anomalies or birth defects
- an important medical event*

*Important medical events are those that may not be immediately life threatening but are clearly of major clinical significance.

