9.2. Adverse Events of Interest

The following adverse events are anticipated in patients with chronic pain, opioid use, or treatment with the trial interventions, and will be considered AEs of Interest.

- Development of suicidality – based on response to question 9 of the PHQ-9
- Development of opioid use disorder or other substance use disorder
- Adverse effect from a medication started during the trial (including buprenorphine) to treat pain, opioid dependence, depression, or anxiety
- Falls
- Withdrawal symptoms
- Dental events in participants who have switched to buprenorphine

AEs of Interest will be ascertained during the contacts between the research coordinator and the participant that occur every 4 weeks through specific questioning and, as appropriate, by review of medical records. Information about the events will be recorded on the Adverse Event of Interest case report form (CRF) and entered into the data management system.

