10.2.3.2 Analyses of the Secondary Endpoints

The secondary endpoints include pain severity, pain catastrophizing, opioid use, other PROs, hospitalizations, falls and mortality.

For continuous endpoints, such as pain severity, pain catastrophizing, and opioid use expressed as MME/day., similar methods as described for the primary outcome will be used to compare differences in changes of the endpoints between PCST and Usual Care at 12 (**Table 10.1; Question 1**), 24 (**Table 10.1; Question 2**), and 36 (**Table 10.1; Question 3**) weeks; i.e., linear mixed effects models with adjustment for baseline measures (and additional adjustment for buprenorphine eligibility and initiation of buprenorphine for **Question 3 in Table 10.1**), taking into account the repeated measures over time and clustering of recruitment sites via random effects.

For binary endpoints, such as the composite of pain interference and opioid use, generalized linear mixed effects models with a binomial distribution and a log link adjusting for baseline measures (additionally adjusting for buprenorphine eligibility and initiation of buprenorphine for **Question 3 in Table 10.1**), taking into account the repeated measures over time and clustering of recruitment sites via random effects, will be used to compare relative risks between PCST and Usual Care at 12 (**Table 10.1; Question 1**), 24 (**Table 10.1; Question 2**), and 36 (**Table 10.1; Question 3**) weeks.

For recurrent endpoints (counts) such as number of hospitalizations and falls, participants will be followed from baseline to 36 weeks, loss-to-follow-up, or death, whichever comes first. Generalized linear mixed effects models with a Poisson distribution, an offset of follow-up time and a log link adjusting for baseline measures (additionally adjusting for buprenorphine eligibility and initiation of buprenorphine for **Question 3 in Table 10.1**) will be used to compare event rates between PCST and Usual Care during the Phase 1 study period (**Table 10.1; Questions 1 – 3**). Repeated measures over time and clustering of recruitment sites will be taken into account via random effects.

For time to event endpoints such as mortality, participants will be followed from baseline to 36 weeks, loss-to-follow-up, or death, whichever comes first. Cox proportional hazards models will be used to compare risks of

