10.4. Safety Analyses

Proportions of participants with at least one adverse event and rates of adverse events will be determined. Differences between the PCST and Usual Care groups in the proportions and the rates will be compared using logistic regression models and Poisson regression models, respectively, adjusting for baseline measures. For participants who switch to buprenorphine, adverse events occurring during the buprenorphine phase (Weeks 24-36) will also be summarized.

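### Section 10.4 compares adverse-event rates by Poisson regression with no stated allowance for repeat events in one participant; with ordinary standard errors the intervals would be too narrow, modestly so for falls on the protocol's own figures

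*Combined protocol and SAP*

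**What the plan says.** Section 10.4 plans two between-arm safety comparisons: the proportion of participants with at least one adverse event, and the adverse-event rate. They "will be compared using logistic regression models and Poisson regression models, respectively, adjusting for baseline measures". The general rule in Section 10.2.2 adds adjustment for site and baseline opioid use. Neither section says how several events in one participant enter the variance of the rate comparison, and 10.4 gives no offset.

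Falls appear in two roles. Section 9.2 lists them among events "anticipated in patients with chronic pain, opioid use, or treatment with the trial interventions, and will be considered AEs of Interest", and Section 4.2.2.3 makes them a secondary outcome. Both are collected at the same four-weekly contacts (Sections 7.4.2 and 7.5.2). For falls as a secondary outcome, the section printed as 10.2.3.2 is more complete. It specifies "Generalized linear mixed effects models with a Poisson distribution, an offset of follow-up time and a log link", with random effects for repeated measures and recruitment site. It also plans a time-to-first-fall analysis.

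On fall frequency, Section 2.2.1 reports that "25-30% of hemodialysis patients experience at least one fall per year and 57% of these individuals reported multiple falls".

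**The concern.** Because 10.4 handles participants with at least one event separately, its rate must count every event, including repeats. A Poisson model with model-based standard errors takes the variance of each participant's count to equal its mean, given the covariates. When some people have many events and most have none, the variance exceeds the mean, the reported interval is too short, and the test rejects too often.

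The plan allows for this in 10.2.3.2 but is silent in 10.4. The same falls could therefore be compared between arms under two differently specified models. The safety table could show a nominally significant difference in fall rate, in either direction, that the secondary-outcome analysis does not. The plan does not say which result governs.

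**Working it through.** Section 10.4 gives no figure to reproduce. The check asks whether the protocol's fall figures fit a Poisson count and, if not, what the smallest distortion is.

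**Inputs.** Yearly risk of at least one fall, p = 0.25 to 0.30 (midpoint 0.275), and share of fallers with more than one fall, 0.57 (Section 2.2.1). Follow-up of 36 weeks. Two-sided 5% level (Section 10.2.2). 320 per arm (640 in two arms).

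**Step 1: repeat fallers under a common-rate Poisson.** With μ = -ln(1 - p), the share of fallers who fall more than once is 1 - μ(1 - p)/p. For p = 0.25, μ = 0.2877 and the share is 1 - 0.2877 × 0.75/0.25 = 0.137. The reported 0.57 is several times larger, so these counts are overdispersed.

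**Step 2: smallest overdispersion consistent with the figures.** Let every repeat faller fall exactly twice. Moving any of them to three or more raises the variance-to-mean ratio, so this is a floor. Then M = 0.43p + 2 × 0.57p and V = 0.43p + 4 × 0.57p - M². For p = 0.25, M = 0.1075 + 0.2850 = 0.3925, V = 0.1075 + 0.5700 - 0.1541 = 0.5234, and V/M = 1.33.

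**Step 3: scale to 36 weeks.** With falls spread evenly over the year, φ = 1 + (V/M - 1) × 36/52.

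**Step 4: effect on inference.** Reported width relative to correct width = 1/√φ. Actual error of the nominal 5% test = 2[1 - Φ(1.96/√φ)].

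| Yearly fall risk | 25% | 27.5% | 30% |
|---|---|---|---|
| Repeat share, common-rate Poisson | 13.7% | 15.2% | 16.8% |
| Repeat share, Section 2.2.1 | 57% | 57% | 57% |
| M per year | 0.3925 | 0.4318 | 0.4710 |
| V/M per year, floor | 1.33 | 1.29 | 1.26 |
| φ at 36 weeks | 1.231 | 1.204 | 1.177 |
| Relative interval width | 0.90 | 0.91 | 0.92 |
| Error at nominal 5% | 7.7% | 7.4% | 7.1% |

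A simulation of 4,000 null trials at the midpoint (floor case, 320 per arm) gave 7.6% error with model-based and 5.4% with robust standard errors.

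**Step 5: covariates.** If adjustment explains a share R of the excess variance, φ - 1 is multiplied by (1 - R). With R = 0.5 the 36-week error is 6.0-6.3%; with R = 0.75 it is 5.5-5.7%. The documents give no value for R; these are assumed.

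**Step 6: an assumed shape.** A negative binomial matched to the same two figures has a yearly V/M of 4.51-4.97. At 36 weeks φ is 3.43-3.75, relative width 0.52-0.54 and error 29-31%. The documents do not support this shape over any other.

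**The case against.** The strongest reply is that 10.4 does not describe the analysis quantified above. Read literally, it compares overall adverse-event rates and promises no fall-specific rate ratio. It also does not say that model-based standard errors will be used, and Poisson regression is compatible with a robust variance. Both statements are correct. The size given is therefore conditional, and none can be given for the pooled rate, because the documents contain no recurrence figure for it. The direction still holds for any recurrent event analysed in the ordinary way, and leaving the variance method open means that it could be chosen after the data are seen.

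A second reply is that nothing depends on it. Falls already have a mixed model and a time-to-first-fall analysis, the stopping rules concern the primary objective, and the logistic comparison is unaffected by repeats. This stands, and it limits the severity.

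Three stronger readings are tempting, but the documents do not support them:

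- **That the false-positive rate is near 30%.** This needs the negative binomial shape of Step 6.
- **That hospitalizations are distorted to a known degree.** An adverse event that "requires or prolongs hospital stay" is serious (Section 9.1.2), so hospital stays can enter an adverse-event count. But 10.4 plans no hospitalization count, and no recurrence figure is given.
- **That adverse events have no time window.** Section 9.1.5 runs reporting to study completion, and the schedule in Appendix 14.1 has adverse events ascertained through Week 36. What 10.4 lacks is a statement that its rates use that period, with an offset.

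**Conclusion.** The concern holds in a limited form, and its severity is minor. Section 10.4 specifies a Poisson comparison of recurrent events without saying how repeats are allowed for, and its ordinary implementation gives intervals that are too narrow.

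For falls, the size that the documents support is the unadjusted 36-week floor of Step 4, which is lower if covariates absorb some of the excess variance. It rests on these assumptions: falls are compared under 10.4 with model-based standard errors; the 57% refers to the same year as the 25-30%; these background figures apply to this sample; falls are spread evenly over the year; and there is no dropout.

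The consequence is at most a safety-table result for falls that disagrees with the secondary-outcome analysis.

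**What to change.** In Section 10.4, state that the Poisson rate models use participant-level robust (sandwich) standard errors and a log follow-up-time offset, over the adverse-event period already set in Section 9.1.5 and Appendix 14.1 (to Week 36). Add that, for falls, the rate analysis in Section 10.2.3.2 is the governing comparison.

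Separately, 10.2.3.2 should reconcile its own period. It says "For recurrent endpoints (counts) such as number of hospitalizations and falls, participants will be followed from baseline to 36 weeks", yet compares event rates "between PCST and Usual Care during the Phase 1 study period", and Section 4.1 defines Phase 1 as Weeks 1-24.

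This takes a sentence or two in 10.4 and a correction in 10.2.3.2; no new data are needed. The price is a modestly wider safety interval. At 320 per arm and 27.5% fallers per year, the floor case expects 320 × 0.43175 × 36/52 = 95.6 falls per arm over 36 weeks. The model-based standard error of the log rate ratio is √(2/95.6) = 0.145, a 95% margin of exp(1.96 × 0.145) = 1.33 as a factor. The corrected standard error is 0.145 × √1.204 = 0.159, a factor of about 1.36 to 1.37.

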6. STUDY INTERVENTIONS

[figure not shown]

Figure 1.1 and described in **Section 4.1**, participants will be initially randomized to Pain Coping Skills Training for 24 weeks, or Usual Care. At Week 24, all participants will be assessed for eligibility for the buprenorphine intervention. Buprenorphine-eligible participants – determined by current opioid use, will be encouraged, but not required, to switch from their full agonist opioid medication to buprenorphine.

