6.2.7.1. Traditional Method for Initiating Buprenorphine

For the traditional method, full-agonist opioids are stopped entirely prior to starting buprenorphine. The interval between last dose of the full-agonist opioid and the first dose of buprenorphine depends on the duration of action of the full-agonist opioid. In most cases, 12-18 hours is appropriate for short-acting opioids. For long-acting opioids, a longer interval is typically needed (approximately 18-24 hours for morphine SA). Patients using the traditional method for switching to buprenorphine will be advised that they will experience opioid withdrawal symptoms during the interval after stopping full-agonist opioids and before starting buprenorphine. For participants using long-acting opioids (e.g., oxycodone controlled-release, morphine controlled-release tablet or capsule, oxycodone controlled-release, oxymorphone extended-release hydromorphone extended-release, fentanyl transdermal), the crossover method will be used rather than the traditional method in order to avoid the need for prolonged periods without use of either the full agonist opioid or buprenorphine.

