6.2.7.3. Information for Participants About Initiation of Buprenorphine

Precipitated opioid withdrawal is the main potential adverse effect of switching to buprenorphine; however, this can be avoided by adhering to the initiation protocol. When using the traditional method for switching to buprenorphine, the most critical point patients need to understand is that the full agonist opioids must be sufficiently cleared from the body before buprenorphine initiation. This means that participants must wait for the onset of at least moderate withdrawal symptoms. When using the crossover titration method, the critical point is to start at a very low dose and increase according to instructions over several days. All patients will be provided detailed written and verbal information about opioid withdrawal symptoms and about precipitated withdrawal. Understanding will be confirmed by teach-back.

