6.2.7.4. Initial Visit with Buprenorphine Prescriber

Participants who meet eligibility criteria for the Phase 2 buprenorphine intervention will be scheduled as soon as convenient for a visit (in-person or by video) with a study physician who will prescribe the buprenorphine. Substance use testing using saliva will be performed prior to the initial visit with the buprenorphine prescriber.

The initial buprenorphine visit will be an in-person or video-based visit with the study buprenorphine prescriber, as described above. First visit tasks include the following:

- Obtain history of prescription and non-prescription opioid use and substance (alcohol, drug) use and assess for substance use disorder; assess buprenorphine risk factors (including risk for pregnancy if applicable)
- Provide standardized buprenorphine educational materials and resources
- Discuss benefits and risks of buprenorphine use and provide instructions to reduce risks such as dental problems
- Recommend buprenorphine and use shared decision-making to establish a plan for buprenorphine initiation and follow up; provide information about who should be contacted if problems or concerns occur between visits
- Complete informed consent process for initiating buprenorphine

Buprenorphine administration will not occur at the initial buprenorphine visit. After the initial visit has been completed and written informed consent is obtained, the study physician will prescribe buprenorphine, which will be mailed to the patient's home. Patients will self-administer buprenorphine, typically at home, as described above.

Following buprenorphine initiation, structured follow-up will occur at multiple time points within the first 3 weeks after buprenorphine initiation. These follow-up visits will occur at 2-3 days, 1 week, 2 weeks, and 3 weeks after initiation, but the timing can be modified based on the judgement of the buprenorphine

prescriber. These visits will be conducted by the buprenorphine-prescribing study physician. Most visits will be conducted by telephone, but they may be conducted in-person or by video if preferred. After these four structured visits, follow up will occur at a frequency determined by the buprenorphine prescriber but will include follow-up at Weeks 32 and 36 during which plans for post-trial pain management will be discussed (see Section 6.2.9). Follow-up visit tasks include the following:

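### The adverse-event summary for participants who switch to buprenorphine covers calendar Weeks 24-36, so it mixes time before, on and after the drug

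*Combined protocol and SAP*

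**What the plan says.** Section 10.4 compares adverse events between PCST and Usual Care, and adds one sentence on buprenorphine: for participants who switch, "adverse events occurring during the buprenorphine phase (Weeks 24-36) will also be summarized". No section starts the count at first dose or defines a treatment-emergent event. The general reporting period in Section 9.1.5 covers the whole study.

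The steps to first dose are set out elsewhere. Section 6 states: "At Week 24, all participants will be assessed for eligibility for the buprenorphine intervention". Section 6.2.7.4 then calls for a visit with the prescriber, with no deadline, and says of it: "Buprenorphine administration will not occur at the initial buprenorphine visit". After that visit and written consent, "the study physician will prescribe buprenorphine, which will be mailed" to the participant's home.

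Under the traditional method (Section 6.2.7.1), "full-agonist opioids are stopped entirely prior to starting buprenorphine". Section 6.2.7.3 adds: "This means that participants must wait for the onset of at least moderate withdrawal symptoms". Section 9.2 lists "Withdrawal symptoms" among the Adverse Events of Interest without qualification, whereas it limits dental events in the same list to participants who have switched.

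At the other end of the window, Section 8.1 keeps participants who go back to full agonists in the buprenorphine arm. Section 6.2.9 allows tapering off, or rotating back, during the study.

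**The concern.** A reader of the buprenorphine safety table will take it as describing people on buprenorphine. Read literally, Section 10.4 also counts events that happened on the previous opioid, during the changeover, and after buprenorphine was stopped. Withdrawal is the sharpest case. Under one of the two initiation methods it is a precondition for the first dose, yet it carries the same event label as withdrawal that arises later.

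Table 3.1 justifies Phase 2 by the need for acceptability and tolerability data before large definitive trials in hemodialysis. The safety table will be read for that purpose, and Tables 10.6 to 10.8 contemplate as few as 5 initiators. At such numbers a few misplaced events change the picture.

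**Working it through.** Section 10.4 gives no rate, sample size or power figure to reproduce. The check asks whether the window must contain unexposed time, how much, and what that does to a rate.

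**1. Can first dose fall at the start of the window?** No. Eligibility is assessed at Week 24, the prescriber visit follows, no drug is given at that visit, and supply is mailed afterwards (Sections 6 and 6.2.7.4). The lag is above zero but its length is not stated.

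**2. Range for the lag (assumed).** Section 6.2.7.4 places four structured visits after initiation, the last at 3 weeks, and then follow-up at Weeks 32 and 36. Fitting the four visits in by Week 32 puts first dose no later than about Week 32 − 3 = 29, a lag of 29 − 24 = 5 weeks. The prescriber may change the visit timing, so this is a guide and not a limit. I use 1 to 5 weeks; a lag under one week gives a share below the first row.

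**3. Unexposed share and effect on a rate.** With lag L, f = L/12. If r0 is the pre-dose event rate and r1 the on-drug rate, the window rate is f·r0 + (1 − f)·r1. With R = r1/r0, its relative error as an estimate of r1 is f·(1/R − 1). R is assumed, withdrawal from the switch is left out, and participants are taken to stay on the drug to Week 36.

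| Assumed lag (weeks) | Unexposed share L/12 | Error if R = 2 | Error if R = 0.5 |
|---|---|---|---|
| 1 | 8.3% | −4.2% | +8.3% |
| 2 | 16.7% | −8.3% | +16.7% |
| 3 | 25.0% | −12.5% | +25.0% |
| 4 | 33.3% | −16.7% | +33.3% |
| 5 | 41.7% | −20.8% | +41.7% |

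If R = 1 there is no error. The direction cannot be known in advance.

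**4. Withdrawal before first dose.** For short-acting opioids Section 6.2.7.1 gives an interval of 12 to 18 hours in most cases. The window is 12 × 7 × 24 = 2,016 hours, so the interval is 12/2,016 = 0.6% to 18/2,016 = 0.9% of it. It is negligible as time, but each traditional-method user is expected to have an event in it. If the table shows the proportion with at least one event, each such user can add up to 1/n: 20 percentage points with 5 initiators, 10 with 10, and 5 with 20 (initiator numbers from Table 10.8).

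**5. Time after stopping.** Table 10.7 illustrates 60% of initiators continuing to Week 36. In that illustration 1 − 0.60 = 40% stop earlier, for example 8 of 20, and their later events still fall in the window.

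**The case against.** The strongest reply is that Section 10.4 promises switchers only a summary. It specifies no proportion, denominator or pooling for them, and the modelled proportions and rates are for PCST against Usual Care. Phase 2 is exploratory. Tolerability is defined as not discontinuing for adverse effects among initiators (Sections 4.2.2.4 and 10.3.2), side effects are collected by questionnaire, and the visits in the first 3 weeks after initiation assess withdrawal directly. None of these uses the Weeks 24-36 window. All of this stands, and it limits the weight of the point. It does not change the one window that the plan does state.

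Four stronger readings are tempting, and the documents do not support them:

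- **A large share of switchers must have an event before any drug.** The share using the traditional method is not given. Section 6.2.7 prefers crossover titration and requires it for users of long-acting opioids, so the share could be close to zero.
- **Precipitated withdrawal is necessarily merged with the withdrawal required before first dose.** Section 9.2 has a separate item for harm from medicines begun during the trial, buprenorphine included, and precipitated withdrawal could be recorded there. What is missing is a rule that says so.
- **Starting the count at first dose would cure the problem.** Withdrawal after stopping the full agonist is a harm of switching, and switching is the intervention. A plain first-dose window would drop it, and a single pre-dose category would pool it with unrelated events.
- **Withdrawal after first dose is precipitated withdrawal.** Under crossover the full agonist is stopped days after buprenorphine begins (Section 6.2.7.2), and Section 6.2.10 links withdrawal symptoms to changes in CYP3A4 medication. Timing alone does not settle the cause.

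**Conclusion.** The point holds as a reporting defect in an exploratory, descriptive table. That the Weeks 24-36 window contains time before first dose follows from the text alone. For participants who stop early, it also contains time after the last dose.

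The size rests on assumptions. The unexposed share is about 8% to 42% for lags of 1 to 5 weeks. The resulting error in an on-drug event rate runs from none, through an understatement of 4% to 21% if the on-drug rate is double the pre-dose rate, to an overstatement of 8% to 42% if it is half. Traditional-method users are expected to have a withdrawal event of interest before any buprenorphine, but no figure for their number can be given. The primary and secondary PCST comparisons and the named acceptability and tolerability outcomes are unaffected.

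**What to change.** In Section 10.4, keep the Weeks 24-36 total for switchers and report events, with person-time, for four mutually exclusive periods:

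1. Week 24 to the start of the switch.
2. The switch itself, from the earlier to the later of the last full-agonist dose and the first buprenorphine dose, so that one definition serves both initiation methods.
3. On buprenorphine.
4. After the last buprenorphine dose.

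For the switch period, lead with the number of participants affected, since a rate over hours or a few days says little. Show withdrawal events by period and initiation method. Have the investigator classify precipitated withdrawal rather than inferring it from timing, and state which Section 9.2 item it is recorded under.

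The cost is smaller cells and possibly an added form field. Section 9.4.2 lists onset date for SAE reports. The Adverse Event of Interest form is not among the documents and these events are ascertained every 4 weeks, so onset date should be added if it is not already there. First-dose date has to be known to schedule the visit 2 to 3 days after initiation; whether the date of the last full-agonist dose is recorded should be confirmed. No visit and no aspect of clinical management changes.
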